7.2 General Principles

By-subject listings will be created for each eCRF module. Summary tables for continuous variables will contain the following statistics: N, mean, median, standard deviation, standard error, minimum, maximum, and 95% confidence interval (CI) as appropriate. Summary tables for categorical variables will include N, percentage, and 95% CIs on the percentage, as appropriate. Confidence intervals for proportions, when provided, will be calculated using the Clopper-Pearson exact method (Clopper 1934). Graphical techniques will be used when such methods are appropriate and informative. For safety summaries, CIs will not be presented, unless specified otherwise. Tables will separate data by treatment arm.

Transformations of the data may be explored if warranted by the distribution of the data. Analyses resulting from transformations applied after the data are unmasked will be considered to be exploratory.

The primary efficacy analyses are based on percent changes in the MNREAD Maximum Reading Speed endpoint at Week 48, the period where the double-masked randomized phase of the study will end. Hypotheses are stated to test for differences in this clinical outcome relative to baseline between ataluren-treated and placebo-treated subjects at this time. At Week 48, subjects will proceed to the open-open label Stage 2 of the study until week 96, where subjects originally on placebo will receive ataluren. Subsequent to Week 96, subjects will have the option of continuing study drug (ataluren) through Week 144. Descriptive statistics will be provided for all visits till Week 144 for all efficacy endpoints by placebo and ataluren treatment groups. In addition, all descriptive statistics for combined ataluren treatment will also be provided till Week 144. For the latter analysis the baseline for placebo group will be Week 48 value.

Differences in non-visit specific safety data, for example, AE and concomitant medication, will be compared directly between ataluren-treated and placebo-treated subjects during the first stage of the study, through Week 48. Ataluren experience during the whole study will also be displayed. For visit specific data, for example, lab data, similar analysis will be performed as for efficacy data except no hypothesis testing will be performed.

Unless otherwise specified, all analyses will be 2-sided at the 0.05 level of significance.

All analyses will be performed using SAS® Software (Version 9.4, or later) ([SAS Institute Inc. 1990](#)).

7.3 Study Population

7.3.1 Subject Disposition

The number of subjects who are screened, randomized, receive study drug, and complete each study stage will be summarized. The number of subjects included in the safety/ITT, and efficacy analysis populations will be included in the table. Attendance at each visit, including missed visits, discontinuations, lost to follow-up, and percentage accountability will be summarized. Accountability is determined by dividing the number of subjects attending a visit by the sum of those who attended the visit, who missed the visit, or who were lost to follow-up at the visit). Subjects discontinued or who have not yet reached the visit of interest, are not counted in the denominator. The formula would read:

$$\% \text{ Accountability} = 100 * (\text{number attending visit} / (\text{number attending visit} + \text{number missing visit} + \text{number lost to follow-up}))$$

A list of subjects who withdraw early will be provided. This listing will include the reason and timing of the withdrawal. Similarly, the reason any subject is excluded from an analysis set will also be provided. In addition, significant known protocol deviations will be noted for individual subjects; a summary table may also be provided for these deviations.

7.3.2 Demographic and Baseline Characteristics

Age, race, ethnicity, sex, height, weight, body mass index, and medical history will be summarized by treatment arm for ITT subjects receiving study drug, using descriptive statistics.

7.3.3 Medical History and Prior Medication

Medical history and prior medication information will be summarized.

7.4 Extent of Exposure

7.4.1 Defining Rules

The extent of exposure to ataluren treatment is defined as the last dose date minus the first dose date + 1 day. The frequency will be presented according to the duration ranges as follows:

The extent of exposure to ataluren treatment is defined as the last dose date minus the first dose date + 1 day. The frequency will be presented according to the duration ranges in each Stage (i.e., Stage 1 [double-masked dosing] or Stage 2 [open-label dosing]): <24 weeks, >24 to <48 weeks, >48 to <72 weeks, >72 to <96 weeks, >96 to <120 weeks, >120 to <144 weeks, and ≥ 144 to <168 weeks, ≥ 168 to <192 weeks, ≥ 192 to <216 weeks, and ≥ 216 to ≥ 240 weeks. Descriptive statistics (mean, standard deviation, median, min, max) will be presented for Stage 1, Stage 2, Week 144 – end of the study, and the whole study.

7.4.2 Study Drug Compliance

Study drug compliance will be assessed by analysis of unused study drug reported. Compliance will be summarized by treatment arm in terms of the percentage of drug actually taken, as reported by the subject, relative to the amount that should have been taken during the study, per the protocol.

Based on the mg total from number of color-coded sachets prescribed (125 mg in yellow, 250 mg in pink, and 1000 mg in blue), the protocol-specified dose will be calculated for each subject at each administration. The amount in mg reported taken by the subject will be recorded. The sum of the reported mg taken, divided by the mg prescribed, will be the basis upon which percentage compliance is calculated.

The numerator and denominator are based on these calculations

The amount taken (numerator) is the sum of

(Number of tablets distributed – number of tablets remained in 125 mg sachets)*125,
(Number of tablets distributed – number of tablets remained in 250 mg sachets)*250, and
(Number of tablets distributed – number of tablets remained in 1000 mg sachets)*1000.

Protocol specified sum to be taken (denominator) is calculated using the rules below.

The amount supposed to be taken between Visit i and Visit i+1 is

$m_i = (\text{weight at Visit } i) * 40 * (\text{number of days between Visit } i \text{ and Visit } i+1)$

The amount supposed to be taken in a period (for example, stage 1) is the sum of m_i for the visits in the period.

Compliance will be assessed in Stage 1, Stage 2 and the entire study.

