#### **6.1.4 Study Drug Dispensing**

During the parent study (masked Stage 1 and open-label Stage 2) and the sub-study, dosing of ataluren will be based on milligrams of drug per kilogram of subject body weight and will be adjusted to allow for dosing with up to 2 of the available sachet dose strengths (125 mg, 250 mg, and/or 1000 mg). The sachet dose strengths and number of sachets to be taken per dose will be calculated and provided by the IVR/IWR system.

The clinic staff (e.g., pharmacist or other qualified person) will be responsible for dispensing study drug according to the IVR/IWR system directions. At the time of randomization, the IVR/IWR system will provide the clinic staff with the subject randomization number and the kit ID numbers designating the kits to be dispensed. Multiple kits may be dispensed at a single visit (maximum of two different strengths).

The clinic staff (e.g., pharmacist or other qualified person) will write the subject number on each kit that is dispensed. A 180-day supply (2 kits each containing 90 sachets; 24 weeks + 6 days) of study drug will be provided for each two 24-week study periods of Stage 1, the four 24-week study periods of Stage 2, and the four 24-week study periods during the sub-study.

Because of potential changes in subject body weight over time, at Week 24 (Visit 3) and every 24 weeks thereafter, a dose adjustment will be made based on the subject's body weight at that visit. Depending upon the magnitude of change in subject body weight since baseline, the number and strengths of sachets to be used by the subject may remain the same or may be adjusted.

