#### **6.2.2 Drug Administration Plan**

Study drug (masked ataluren or placebo [during Stage 1] as well as open-label ataluren [during Stage 2 and the sub-study]) will be administered TID. The dose level to be administered is: 10 mg/kg in the morning, 10 mg/kg at midday, and 20 mg/kg in the evening.

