#### **6.2.5 Study Drug Preparation and Storage**

Once at the investigational site and/or with the subject/caregiver, study drug sachets should be stored at room temperature, away from the reach of children until time of reconstitution and should only be opened at the time of dose preparation. The full contents of the sachets should be mixed with at least 30 mL (1 ounce) of liquid (water, milk, fruit juice, fruit punch), or 3 tablespoons of semi-solid food (yogurt, pudding, or applesauce). The prepared dose should be mixed well before administration. The amount of the liquid can be increased based on subject preference.

Each prepared dose is best administered immediately after preparation. The prepared dose should be discarded if not consumed within 24 hours of preparation (if kept refrigerated), or within 3 hours of preparation (if kept at room temperature).

The clinic staff will instruct each subject or parent/caregiver on the specific number of sachets to be taken from each kit for each dose and will provide detailed oral directions regarding drug preparation. In addition, detailed written drug mixing and dosing instructions will be provided to the subject or parent/caregiver when drug supplies are dispensed. A copy of these instructions will be maintained in the investigator site study file.

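### SAP 7.4.2 defines compliance against mg prescribed but computes it against weight × 40 × days, so the percentage mixes adherence with sachet rounding (wrong as written, minor)

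*SAP*

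**What the plan says.** SAP 7.4.2 first describes compliance in words. The dose at each administration is worked out "Based on the mg total from number of color-coded sachets prescribed", and "The sum of the reported mg taken, divided by the mg prescribed, will be the basis upon which percentage compliance is calculated". The denominator described there is the sachet amount the subject was told to take.

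The same section then sets out the calculation. The numerator counts units distributed minus units remaining, each multiplied by its sachet strength; the units are called tablets. Of the denominator it says: "Protocol specified sum to be taken (denominator) is calculated using the rules below". The rule is weight at Visit i × 40 × the days from Visit i to the next visit, summed over the visits in the period. It has no sachet term.

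The protocol explains why the two amounts differ. Section 6.2.2 sets the nominal dose at "10 mg/kg in the morning, 10 mg/kg at midday, and 20 mg/kg in the evening". Section 6.1.4 says that weight-based dosing "will be adjusted to allow for dosing with up to 2 of the available sachet dose strengths", and leaves the choice of sachets for each dose to the IVR/IWR system. Section 6.2.5 has the whole sachet used: "The full contents of the sachets should be mixed with at least 30 mL". Protocol 11.6.1 relates drug taken to the amount that should have been taken, without a formula, so it does not settle which denominator is meant.

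**The concern.** Available doses come in whole sachets of 125, 250 or 1000 mg, so every dose is a multiple of 125 mg. The numerator in SAP 7.4.2 counts those whole sachets, while the denominator uses the exact mg/kg target. The ratio therefore departs from 100% for two reasons that cannot be separated afterwards: missed doses, and the gap between the assigned sachets and the exact target. A subject who took everything can appear to have missed drug, and one who missed drug can appear complete.

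What is at stake is whether the reported figure can be read as adherence, both for each subject and as a level in each arm. The relative gap is largest at low body weight, where one 125 mg step is a large share of a dose, and Protocol 4.2 admits subjects from 12 kg.

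**Working it through.** **Inputs**
- Dose per administration: 10, 10 and 20 mg/kg (Protocol 6.2.2).
- Sachet strengths: 125, 250 and 1000 mg (Protocol 6.1.1), all multiples of 125 mg.
- Whole sachets used (Protocol 6.2.5).
- Minimum weight: 12 kg (Protocol 4.2).
- Rounding rule: not in the documents. Nearest 125 mg per dose is assumed, with rounding up and rounding down also shown.

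**The plan's own figure.** 10 + 10 + 20 = 40 mg/kg/day, the multiplier in SAP 7.4.2. The overdose definition in Protocol 6.1.8 agrees: 160 / 4 = 40.

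**Formula.** Let r() be rounding to a multiple of 125 mg and w the weight in kg. Days appear in both numerator and denominator and cancel. A subject who takes every assigned sachet scores

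[2 × r(10w) + r(20w)] / (40w)

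**Nearest 125 mg, constant weight**

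| Weight (kg) | Sachet mg per day | 40w | Score at full adherence |
|---|---|---|---|
| 12 | 125 + 125 + 250 = 500 | 480 | 104.2% |
| 15.5 | 125 + 125 + 250 = 500 | 620 | 80.6% |
| 19 | 250 + 250 + 375 = 875 | 760 | 115.1% |
| 25 | 250 + 250 + 500 = 1000 | 1000 | 100.0% |
| 30 | 250 + 250 + 625 = 1125 | 1200 | 93.8% |
| 31 | 250 + 250 + 625 = 1125 | 1240 | 90.7% |
| 31.5 | 375 + 375 + 625 = 1375 | 1260 | 109.1% |

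On a half-kilogram grid, 80.6% and 115.1% are the extremes over 12 to 20 kg, and 90.7% and 109.1% are the extremes over 30 to 80 kg. At 19 kg, a subject who took 760 of 875 mg per day would have missed 1 − 760/875 = 13.1% of the assigned drug and would still score 100%.

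**Other rounding rules, 12 to 20 kg, half-kilogram grid**
- Rounding up: 100% to 168.3%. The maximum is at 13 kg: 250 + 250 + 375 = 875, against 520.
- Rounding down, with at least one sachet per dose: 67.6% to 100%. The minimum is at 18.5 kg: 125 + 125 + 250 = 500, against 740.

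Rounding up can only give 100% or more, and rounding down 100% or less, apart from any one-sachet minimum. The unstated rule therefore decides the direction and size of the distortion, but some distortion is present under each.

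**Weight change within Stage 1.** Weight is updated every 24 weeks for both dosing and the denominator. With two equal intervals and nearest rounding:
- 15.5 then 16.5 kg: (500 + 625) / (40 × 32) = 1125/1280 = 87.9%.
- 18 then 19 kg: (625 + 875) / (40 × 37) = 1500/1480 = 101.4%.

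**With the denominator the SAP describes in words.** Sachet mg assigned divided by sachet mg assigned is 100% at every weight under any rounding rule, for example 500/500 at 15.5 kg.

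**The case against.** The strongest reply is that only one formula in SAP 7.4.2 can be programmed, so there is no real ambiguity, and that drug received relative to the mg/kg target is a legitimate quantity. On that view the prose is merely mislabelled. Part of this stands: weight × 40 × days does measure dose received against target. But the section says it is measuring drug taken against drug prescribed, and the formula does not return that.

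The second reply is that nothing depends on the number. This stands. Compliance is only summarised by arm. Neither document sets a compliance threshold, defines an analysis set by compliance (Protocol 11.2, SAP 6), or uses it in an efficacy model (SAP 7.7). The withdrawal provision for noncompliance in Protocol 10 cites no percentage.

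A reader might infer three stronger things that the documents do not support.
- That the error undermines interpretation of a null Week 48 result. The primary endpoint is MNREAD reading speed, and Protocol 8.3.15 does not require the test under 8 years. The children at 15 to 19 kg are probably mostly under that age, although the documents give no weight-for-age data.
- That 81% to 115% is what the trial will report. Those are extremes at fixed low weights under an assumed rounding rule. Some weights score 100%, and growth between visits can average the error down.
- That the arm comparison is biased. Placebo sachets match the active strengths (Protocol 6.1.2), so both arms carry the same form of error with no evident direction. Chance imbalance is possible: with the 24 subjects in SAP 2.5 and 2:1 allocation, about 8 are on placebo, and one fully adherent subject at 80.6% lowers that arm's mean by 19.4/8 = 2.4 points. That is noise in a descriptive table, not systematic bias.

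**Conclusion.** The point holds as a minor error: wrong as written. SAP 7.4.2 describes one denominator and computes another, and because dosing is in whole sachets the two generally differ. The computed percentage is not a clean measure of adherence.

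Under the assumption of nearest-125-mg rounding per dose, full adherence scores between about 81% and 115% at the low-weight extremes and about 91% to 109% at 30 to 80 kg. The true size and direction depend on the IVR/IWR rule, which neither document states. That a fully adherent subject need not score 100% does not depend on the assumption. The consequence is limited to the level and per-subject reading of the compliance summary; no planned estimate, test or analysis set changes.

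**What to change.** In SAP 7.4.2, state one denominator that matches the section's own definition: the sachet mg per day assigned by the IVR/IWR system × days in the interval, summed over the intervals in the period. Replace tablets with sachets in the numerator. If weight × 40 × days is also wanted, report it separately and label it as dose received relative to the mg/kg target.

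The cost is a few lines of SAP text and the matching program specification. The IVR/IWR system already calculates the sachets per dose (Protocol 6.1.4), so no new data collection should be needed. No change to dose or sachet assignment is proposed.

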7.5 Safety Analyses

The safety profile will be based on adverse events, concomitant medications, vital signs, physical examinations, and clinical laboratory measurements. All treated subjects will be included in the safety analyses.

Adverse event and SAE summaries will also be presented for the following periods:

- Through Week 48 (double-masked phase)
- Through End of Treatment (entire study, including the sub-study)

7.5.1 Adverse Events

Adverse events will be grouped by system organ class and by preferred term within system organ class according to the latest version of the Medical Dictionary for Regulatory Activities coding dictionary. The number of subjects reporting at least 1 adverse event will be summarized by treatment group. Tables and/or narratives of any on-study death, serious or significant adverse events, including early withdrawals because of adverse events, will be provided should they occur.

Summary information (the number and percent of subjects by treatment) will be tabulated for:

- Treatment-emergent adverse events, including clinical and laboratory adverse events
- Treatment-related adverse events
- Treatment-emergent adverse events by severity
- Treatment-related adverse events by severity
- SAEs
- Adverse events leading to discontinuation
- Ocular adverse events

Adverse events will be summarized separately through Week 48 (Study Phase 1), from Week 48 through Week 148, through Week 148, and through end of treatment, including sub-study. Adverse events will be assigned to a study phase based on the start date of the adverse event. In study Stage 1 and entire study, AEs will be summarized by treatment. In addition, AEs while subjects are on ataluren will be presented for the entire study.

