## **9.3 Adverse Event Recording**

All adverse events (both serious and non-serious) that occur in subjects during the adverse event reporting period must be recorded, whether or not the event is considered drug related. In addition, any known untoward event that occurs subsequent to the adverse event reporting period that the investigator assesses as possibly related to the investigational drug/product should also be recorded as an adverse event.

All adverse events are to be recorded in the source documents and on the eCRF using concise medical terminology; whenever possible terms contained in the Medical Dictionary for Regulatory Activities (MedDRA) should be employed. In addition, the following information should be recorded:

- Indication of whether the event is serious or non-serious (see Section 9.1.2)
- Relationship to study drug (see Section 9.4)
- Severity of the event (see Section 9.5)
- Onset date
- Resolution date, or date of death
- Action taken
- Outcome of the event

Classification of the event as serious or non-serious determines the reporting procedures to be followed.

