## 9.5 Grading of Severity of Adverse Events

The severity of adverse events will be graded using the CTCAE Version 4.0 (refer to the Study Manual). For each episode, the highest severity grade attained should be reported.

If a CTCAE criterion does not exist, the investigator should use the grade or adjectives: Grade 1 (mild), Grade 2 (moderate), Grade 3 (severe), Grade 4 (life-threatening), or Grade 5 (fatal) to describe the maximum intensity of the adverse event. For purposes of consistency with the CTCAE, these intensity grades are defined in Table 5.

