After the subject's last dose of ataluren, there will be a 4-week post-treatment follow-up period. A primary analyses of the double-masked phase will be conducted after the last subject has completed Week 96.

Subjects who complete the parent study will be eligible to participate in the sub-study. The principal investigator or sub-investigator will discuss the possibility of participation directly with study subjects and/or parent/legal guardian in the clinic.

A schematic of the study design is provided in [Figure 1](#).

Figure 1. STAR Aniridia Study Schematic

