5 DEFINITIONS

Adverse Event

An adverse event (AE) is any untoward medical occurrence associated with the use of a drug (investigational medicinal product) in humans, whether or not it is considered related to the drug. An adverse event can therefore be any unfavorable and unintended sign (including an abnormal laboratory finding), symptom, or disease in a study subject who is administered study drug in this study. A specific list of occurrences that should be reported as AEs is provided in section 9.1.1 of the study protocol. Subjects must be followed for adverse events for at least 28 days after the last dose of ataluren administration, or until any drug-related adverse events and/or ongoing serious adverse events (SAEs) have resolved or become stable, whichever is later. Any event that starts within 35 days (to account for visit window) after last dose of ataluren will be summarized.

Adverse events will be graded for severity using Common Terminology Criteria for Adverse Events (CTCAE) Version 4 grading, where 1=Mild, 2=Moderate, 3=Severe, 4=Life-threatening, and 5=Fatal.

Relationship to study treatment will be coded using the following categories: Unrelated, Unlikely related, Possibly related, and Probably related. In summaries where relatedness is dichotomized to related or not, Unrelated and Unlikely related will be classified as not related and Possibly related and Probably related will be classified as related.

Serious Adverse Event:

A serious adverse event is defined as an adverse event that

- Results in death
- Is life-threatening (patient is at immediate risk of death from the event as it occurred)
- Requires in-patient hospitalization (formal admission to a hospital for medical reasons) or prolongation of existing hospitalization
- Results in persistent or significant disability/incapacity
- Results in a congenital anomaly/birth defect

Treatment-Emergent AE:

A TEAE is any AE that begins or increases in severity after the initial dose of study drug and within 5 weeks of the last dose of study drug.

Age

Subject's age is defined as from date of birth to randomization date. The formula used is (randomization date – date of birth+1) / 365.25.

Ataluren Exposure

The duration of exposure to ataluren treatment is defined as the last dose date minus the first dose date + 1 day.

Baseline

For any variable, unless otherwise defined, baseline is the last assessment taken prior to the first study drug administration.

Change from Baseline

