The arithmetic difference between a post-baseline value and the baseline value:

Change from Baseline = (Post-baseline Value – Baseline Value)

Percentage Change from Baseline = [(Post-baseline Value – Baseline Value) / Baseline Value] x 100

End of Double-masked study period

End of double-masked study period is at Week 48 (day 337 ± 28 days), unless terminated early.

End of Study

End of study is at Week 144 (day 1008 ± 7 days), unless terminated early.

Early termination from study

Early termination would be assigned to the visit whose visit window included the termination date. In the event that an early termination visit does not fall within a nominal visit window, then the termination visit will be assigned to the visit closest to that date. If duplicate data result from the assignment of a termination visit, then the values measured last will be selected for analysis.

Enrollment date

Enrollment date will be assigned after confirmation of eligibility has been received from PTC Therapeutics, but not after the first day of study drug administration.

Study drug

Study drug in this study is ataluren (PTC124) or placebo.

Randomization date

Randomization date is the day the subject is assigned a randomization number on study Day 1.

Study Day 1

Day 1 is defined as the first day that study drug is administered to the subject.

Study Day

Day on study = Starting from Day 1

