7.5.3 Clinical Laboratory Tests

Summary of observed values and changes from baseline (last measurement prior to entering the study) will be summarized at each visit. In addition, for laboratory adverse events, severity will be graded by CTCAE, when such grading is available. The frequency of subjects with values below, within, and above the normal reference range will be also be summarized in shift tables at each visit. Worst CTCAE grade will be presented for Stage 1, Stage 2, Week 144 – end of the study, and over the entire study. A subject having the same abnormality more than once within a time interval will be counted only once based on the worst severity grade observed.

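### A clinical adverse event that starts in Stage 1 and worsens after Week 48 is tabulated in Stage 1 at its open-label grade and is absent from the Week 48–148 table

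*SAP*

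**What the plan says.** - **Phase.** SAP 7.5.1 summarises adverse events through Week 48, from Week 48 to Week 148, through Week 148, and through end of treatment including the sub-study. The allocation rule is: "Adverse events will be assigned to a study phase based on the start date of the adverse event". Stage 1 and entire-study summaries are by treatment and include severity tables. A separate sentence promises a whole-study presentation of events during ataluren exposure, with no inclusion rule.
- **Grade.** Protocol 9.5: "For each episode, the highest severity grade attained should be reported". The items to be recorded in Protocol 9.3 include severity, onset date and resolution date. A date of grade change is not among them.
- **Treatment emergence.** SAP 5: "A TEAE is any AE that begins or increases in severity after the initial dose of study drug". The same section adds: "Study drug in this study is ataluren (PTC124) or placebo".
- **Timing.** SAP 2.4 moves placebo subjects to ataluren after Week 48 and states: "A primary analyses of the double-masked phase will be conducted after the last subject has completed Week 96".
- **Principle.** Protocol 11.8 restricts safety presentations to data belonging to the analysis period in question.
- **Laboratory contrast.** SAP 7.5.3 presents worst CTCAE grade separately for Stage 1, Stage 2, Week 144 onward and overall: "A subject having the same abnormality more than once within a time interval will be counted only once based on the worst severity grade observed".

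**The concern.** The start date fixes the period and the highest grade fixes the severity, but the two can come from different periods and, in the placebo arm, from different treatments. Stage 1 is the only randomised safety comparison. As the rules are written, its severity tables can contain grades reached after everyone has moved to open-label ataluren, and the period in which the worsening happened shows no event.

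The timing gives this room to occur. The masked-phase analysis waits for the last subject's Week 96, so records will already have been updated with open-label grades. The protocol describes aniridia as progressive, with keratopathy in about 80% of eyes and visually significant lens opacities eventually in 50% to 85% of individuals (Protocol 2.1). These are disease frequencies, not adverse event rates, but they make ocular events that span Week 48 plausible. Characterising the safety profile of ataluren is a secondary objective.

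**Working it through.** The plan gives no figure to reproduce, because the point is a counting rule. The check applies the written rules to one hypothetical event and then scales it.

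**Hypothetical event.** A placebo subject has an ocular event that starts at Week 40 (day 40 × 7 = 280) at Grade 1. Open-label ataluren starts at Week 48 (day 337 in the schedule of events). The event reaches Grade 3 at Week 60 (day 60 × 7 = 420).

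| Step | Rules as written | Grade split at the first open-label dose |
|---|---|---|
| Recorded grade | max(1, 3) = 3 | 1 before day 337; 3 after |
| Period | 280 < 337, so Stage 1 | Stage 1 for onset; after Week 48 for worsening |
| Stage 1 severity table | Placebo, Grade 3 | Placebo, Grade 1 |
| Week 48–148 table | 0 events | 1 worsening, Grade 3 |
| On-ataluren presentation | Undefined | Grade 3 |

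**Does the treatment-emergent definition rescue it?** No. It counts an event that "begins or increases in severity after the initial dose of study drug", and study drug includes placebo. A placebo subject's reference point is the first placebo dose, and the switch does not reset it.

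**Could the programmer recover the earlier grade?** Not from the items in Protocol 9.3, which provide one severity and no date of change.

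**Time available for a grade to rise.** 96 − 48 = 48 weeks for the last subject, ignoring visit windows. Earlier enrolees who stay in the study have longer, so 48 weeks is nearer a minimum than a maximum.

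**Scale.** With 2:1 allocation, the placebo arm is 36/3 = 12 at the planned size, or 24/3 = 8 at the reduced size in SAP 2.5. The ataluren arm is 24 or 16.

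- Placebo: 1/12 = 8.3 points; 1/8 = 12.5 points.
- Ataluren: 1/24 = 4.2 points; 1/16 = 6.3 points.

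These are shifts in the Stage 1 rate of Grade 3 or higher events per affected subject who has no other such event in Stage 1. The number of affected subjects cannot be derived from the documents.

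**The case against.** The strongest reply is Protocol 11.8. A Week 60 grade is not Week 48 data, the SAP does not withdraw that principle, and SAP 8 lists no departure from it. On this view the documents do not direct later grades into Stage 1. What stands is that the principle is stated. It is not carried out: the SAP allocates whole events by start date, and the recorded items hold a single grade. The two texts need reconciling.

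A second reply is that an episode is not defined, and that the Study Manual or eCRF instructions, which are not available here, may require a new record on worsening. That is possible. Protocol 9.1.1 does make worsening of a pre-existing illness reportable, but its detailed rule concerns conditions noted at Visit 1, not an adverse event ongoing at Week 48.

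Three stronger readings are tempting, and the documents do not support them:

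- **That the event is left out of the on-ataluren presentation.** The start-date rule is written for study phases. The on-ataluren sentence is separate, and an event that worsens under ataluren could be read as falling within it. It drops out only if the start-date rule is extended to that presentation.
- **That the randomised comparison is biased against placebo.** Within placebo subjects the shift can only raise Stage 1 severity. The same happens to ataluren-arm events that worsen after Week 48, and that arm is twice as large. The net direction between arms is unknown.
- **That laboratory toxicity is hidden in the same way.** SAP 7.5.3 takes worst grade by stage, so a creatinine rise after Week 48 would largely show in Stage 2.

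It is also fair to say that incidence is unaffected, that adverse events are not formally tested (Protocol 11.8), and that by-subject listings, by-visit slit-lamp summaries and narratives for serious or significant events give partial cover.

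**Conclusion.** The point holds for the severity tabulation of clinical and ocular adverse events. As written, an event with onset in Stage 1 that worsens after Week 48 appears in the Stage 1 severity table at its open-label grade and is absent from the Week 48–148 table. This conflicts with Protocol 11.8 and is inconsistent with the by-stage grading of laboratory abnormalities. Inclusion in the on-ataluren presentation is an undefined matter, not an established omission.

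The size is 8.3 or 12.5 points on the placebo severe-event rate per affected subject, with frequency and net direction between arms unknown. The conclusion assumes that one record per episode is kept across Week 48, that no grade-change date is collected beyond the items in Protocol 9.3, and that allocation is close to 2:1. It is worth correcting before the masked-phase analysis, because the remedy is cheap and the table concerned is the only randomised view of severity.

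**What to change.** In SAP 5 and 7.5.1:

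1. Base Stage 1 severity tables, in both arms, on the highest grade reached before the first open-label dose.
2. Define on-ataluren treatment-emergent events as those that start or increase in severity on or after the first ataluren dose. For placebo subjects, worsening after the switch then counts in the Week 48–148 table (when it falls in that span) and in the on-ataluren presentation.

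In the eCRF completion instructions:

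3. For each adverse event ongoing at Visit 4, record the grade at that visit and the highest grade so far. Alternatively, open a new linked record, dated at the increase, when the grade rises after the switch. The linked record also separates worsening in Stage 2 from worsening in the sub-study. Neither option should enter a resolution date for an event that has not resolved.

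The cost is a few SAP sentences, an eCRF note and queries on events ongoing at Visit 4. For subjects already past Week 48, the earlier grade must come from source documents where available and otherwise be flagged as unknown. A few episodes will appear as two records, so counts of events, as opposed to subjects, need a footnote.
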